Adverse Event Collection/ CTCAE Grading		Х	Х		Х	Х	Х	Х	Section 8.3	 Collect continuously at every visit and throughout the study CTCAE Version 5.0 For long-term follow-up: all SAEs regardless of relationship to study treatment and adverse events possibly related to study treatment will be collected All adverse events possibly related to study drugs or protocol procedures should be followed until they resolve, are no longer considered to be possibly related, become stable or return to baseline, the patient starts a new therapy, the patient expires, or the patient becomes lost to follow-up. The frequency of evaluation is determined according to the judgment of the investigator
Concomitant Medications		Х	x		Х	х	Х		Section 6.5	 At baseline, record prior and concurrent medications Record all pre-medications, supportive care, and concomitant medication continuously at every visit and throughout study
Lab/Diagnostic Tests	Coagulation	Х							Section 10.4 Appendix 4	 Perform at baseline and as clinically indicated Local testing

	Study Period	Baseline	Stu	Study Treatment (Cycle =28 day				ontinuation ow-Up		
	Cycle	Screening	1 a	nd 2	3	4 and Beyond (if Applicable)	Short-Term Follow-Up ^a	Long-Term Follow-Up ^a		
	Visit	0	1,3	2, 4	5	6 and Beyond (if Applicable)	801	802–8XX		
	Relative Day within a Cycle	≤28	Day 1	Day 15° (± 3)	Day 1 (± 3)	Day 1 (± 3)	Day 30 (± 7)	(± 14)		
Procedure Category	Procedure								Protocol Reference	Instructions
	Hematology	Х	Х	х	X	X	Х		Section 10.4 Appendix 4	 Assessments may be performed up to 3 days prior to Day 1 of each cycle Local testing Cycles 1 and 2 Day 15 hematology required for Arms A, C only
	Clinical chemistry	Х	х	x	Х	х	Х		Section 10.4 Appendix 4	 Assessments may be performed up to 3 days prior to Day 1 of each cycle Central testing Cycles 1 and 2 Day 15 clinical chemistry required for Arms A, C only
	FSH and estradiol levels	x				х	Х		See Section 5.1 and Section 10.4	 For Screening: local FSH/E2 testing for women <60 years when needed to confirm post-menopausal status For On study: local estradiol every 3 cycles, starting on Day 1 of Cycle 4 and again at STFU visit, for women whose postmenopausal status is due to GnRH agonist treatment
	Pregnancy test	Х					Х		Section 10.7 Appendix 7	 Local testing For Screening: serum pregnancy test required for women of child-bearing potential For on Study: per local regulations and/or institutional guidelines For Short-Term Follow-Up: local testing for women of child bearing potential

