- c. presented de novo with metastatic disease, with subsequent progression on or after only 1 line of therapy with an AI, alone or in combination with a CDK4/6 inhibitor. Note: Patients may not have received any other prior therapy (other than the aforementioned: AI, alone or in combination with a CDK4/6 inhibitor) in the advanced/metastatic setting.
- 4. Must be deemed appropriate for treatment with ET.

5. If female, have a postmenopausal status due either surgical/natural menopause or ovarian function suppression (OFS) with a gonadotropin-releasing hormone (GnRH) agonist such as goserelin or leuprolide (received monthly and initiated at least 28 days prior to Cycle 1 Day 1).

Note: Participants established on a less frequent (i.e. 3-month) GnRH agonist administration schedule will be permitted, if considered by the investigator to have adequate OFS based on serial estradiol assessments.

Postmenopausal due to surgical/natural menopause requires at least 1 of the following:

- a. prior bilateral oophorectomy
- b. age ≥ 60 years
- c. age <60 years, amenorrheic for at least 12 months (in the absence of chemotherapy, tamoxifen, toremifene, or ovarian suppression), and FSH and estradiol levels in the postmenopausal range using local laboratory thresholds.
- 6. If female and postmenopausal status is due to ovarian suppression, participants must have a negative serum pregnancy test at baseline (within 14 days prior to enrollment) and agree to use highly effective, medically approved precautions to prevent pregnancy (see Section 10.7 Appendix 7) during the study and for 6 months (2 years for patients receiving fulvestrant) following the last dose of study treatment
- 7. If male, must agree to use the following:
 - a. hormone suppression (initiated at least 28 days prior to Cycle 1 Day 1) with a gonadotropin-releasing hormone agonist such as goserelin or leuprolide Note: Participants established on a less frequent (i.e. 3-month) GnRH agonist administration schedule will be permitted, if considered by the investigator to have adequate hormone suppression.
 - b. highly effective methods of birth control and to not donate sperm during the study and for at least 6 months (2 years for patients receiving fulvestrant) following the last dose of study drug(s), or for the duration specified in country requirements, whichever is longer
- 8. Have one of the following as defined by RECIST v1.1 (Eisenhauer et al. 2009; Section 10.3 Appendix 3):
 - Measurable disease

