 - f. arrhythmias that are symptomatic or require treatment (not including patients with rate-controlled atrial fibrillation)
 - g. cerebrovascular accident (stroke) within the last 3 months
 - h. a mean QT interval corrected for heart rate of \geq 470 msec on screening ECG, as calculated using the Fridericia's formula at several consecutive days of assessment
 - i. baseline bradycardia with resting heart rate <60 beats per minute at several consecutive days of assessment
- 24. Have serious preexisting medical conditions that, in the judgment of the investigator, would preclude participation in this study (such as severe renal impairment [for example, estimated creatinine clearance <30 mL/min], pre-existing medical condition of ILD/pneumonitis, severe dyspnea at rest or requiring oxygen therapy, history of major surgical resection involving the stomach or small bowel, or preexisting Crohn's disease or

ulcerative colitis or a preexisting chronic condition resulting in clinically significant diarrhea).

- 25. Have a history of any other cancer (except nonmelanoma skin cancer or carcinoma in-situ of the cervix), unless in complete remission with no therapy for a minimum of 3 years
- 26. Have received an autologous or allogeneic stem cell transplant
- 27. Have active bacterial or fungal infection, or detectable viral infection (for example, human immunodeficiency virus [HIV] or viral hepatitis). Screening is not required for enrollment
- 28. Pregnant, breastfeeding, or expecting to conceive or father children within the projected duration of the trial, starting with the screening visit through 180 days after the last dose of study intervention
- 29. Have initiated bisphosphonates or approved RANK ligand (RANK-L) targeted agents (for example, denosumab) <7 days prior to randomization
- 30. Known allergic reaction against any of the components of the study treatment.

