10.7. Appendix 7: Contraceptive Guidance and Collection of Pregnancy Information

Definitions:

Woman of Childbearing Potential

A woman is considered fertile following menarche and until becoming post-menopausal unless permanently sterile (see below). If fertility is unclear (for example, amenorrhea in adolescents or athletes) and a menstrual cycle cannot be confirmed before first dose of study intervention, additional evaluation should be considered.

Women in the following categories are not considered WOCBP:

- 1. Premenarchal
- 2. Premenopausal female with at least 1 of the following:
 - Documented hysterectomy, or
 - documented bilateral salpingectomy, or
 - documented bilateral oophorectomy.

For individuals with permanent infertility due to an alternate medical cause other than the above, (for example, Müllerian agenesis, androgen insensitivity), investigator discretion should be applied to determining study entry.

Note: determination can come from the site personnel's review of the participant's medical records, medical examination, or medical history interview.

- 3. Postmenopausal female is defined as, women with
 - 12 months of amenorrhea for women >60, with no need for FSH
 - 12 months of amenorrhea for women >40 years old with FSH ≥40 mIU/mL and no other medical condition such as anorexia nervosa and not taking medications during the amenorrhea (for example, oral contraceptives, hormones, gonadotropin-releasing hormone, anti-estrogens, selective estrogen receptor modulators, or chemotherapy that induced amenorrhea). If fertility is unclear, then additional evaluation should be considered.

Contraception Guidance:

Patients with reproductive potential (that is, non-postmenopausal patients) are instructed to use highly effective contraceptive methods. The choice of the most effective and appropriate contraception method is up to the investigator's judgment after discussion with the patient, taking into account age, pregnancy, and other gyneco-obstetrical history, sexual activity, patients' preference, acceptance of the contraception method, and potential adherence.

In patients with breast cancer, the use of estrogen-based hormonal contraception (includes the hormonal IUDs) is contraindicated, and the effect of progestin-based hormonal contraception remains unclear.

The Clinical Trial Facilitation Group has defined highly effective methods of contraception.¹

Highly effective methods include

• intrauterine device

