10.16. Appendix 16: Abbreviations

CFR	Code of Federal Regulations	
CFS	chemotherapy-free survival	
CI	confidence interval	
Complaint	A complaint is any written, electronic, or oral communication that alleges deficiencies related to the identity, quality, purity, durability, reliability, safety, or effectiveness, or performance of a drug or drug delivery system.	
Compliance	Adherence to all study-related, good clinical practice (GCP), and applicable regulatory requirements.	
CR	complete response	
CRF	case report form	
CRP	Clinical research physician: Individual responsible for the medical conduct of the study. Responsibilities of the CRP may be performed by a physician, clinical research scientist, global safety physician, or other medical officer.	
CRS	clinical research scientist	
CSR	clinical study report	
СТ	computed tomography	
CTCAE	Common Terminology Criteria for Adverse Events	
ctDNA	circulating tumor DNA	
СҮР	cytochrome P450	
DLT	dose-limiting toxicities	
DMC	Data Monitoring Committee	
DNA	deoxyribonucleic acid	
ECG	electrocardiogram	
eCFR	electronic case report form	
ECOG	Eastern Cooperative Oncology Group	
Enroll	The act of assigning a participant to a treatment. Participants who are enrolled in the study are those who have been assigned to a treatment.	

ER	estrogen receptor
ER+	estrogen receptor-positive
ERα	estrogen receptor α
EDC	electronic data capture system
EEC	endometrial endometrioid cancer
ERB	Ethical Review Board
ET	endocrine therapy
FES	F-fluoroestradiol
FSH	follicular stimulating hormone
G	grade
GCP	Good Clinical Practice
GDPR	EU General Data Protection Regulation
HER2-	human epidermal growth factor receptor 2 negative
HR	hormone receptor
IB	Investigator's Brochure
ICF	informed consent form
ICH	International Council for Harmonisation
IEC	Independent Ethics Committee
IM	intramuscular
IMP	Investigational Medicinal Product (see also "investigational product")
	A medicinal product which is being tested or used as a reference, including as a placebo, in a clinical trial.
Informed consent	A process by which a participant voluntarily confirms his or her willingness to participate in a particular study, after having been informed of all aspects of the study that are relevant to the participant's decision to participate. Informed consent is documented by means of a written, signed, and dated informed consent form.

INR	international normalized ratio	

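### Criterion 6 is triggered only by ovarian suppression, so some women of childbearing potential under Appendix 7 fall outside its 14-day pregnancy test and 2-year fulvestrant contraception period

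*Protocol*

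**What the plan says.** Protocol Section 5.1, criterion 5c, lets a woman under 60 enter as naturally postmenopausal if she has had 12 months of amenorrhea without chemotherapy, tamoxifen, toremifene or ovarian suppression, "and FSH and estradiol levels in the postmenopausal range using local laboratory thresholds". The only lower age limit is the general one of 18 years in criterion 1.

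Appendix 7 (Section 10.7) treats a woman as fertile until she is postmenopausal, unless she is permanently sterile. For women who are not over 60, its postmenopausal category requires "12 months of amenorrhea for women >40 years old with FSH ≥40 mIU/mL".

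Criterion 6 begins: "If female and postmenopausal status is due to ovarian suppression, participants must have a negative serum pregnancy test at baseline". The test must be "within 14 days prior to enrollment", and highly effective contraception must continue during the study and "for 6 months (2 years for patients receiving fulvestrant) following the last dose of study treatment". The Belgium and Germany addenda (Sections 10.10.1 and 10.10.4) repeat criterion 6 with the same trigger. Appendix 16 defines enrolling as "The act of assigning a participant to a treatment".

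Several other provisions apply to women of childbearing potential whether or not criterion 6 does:
- The Schedule of Activities (Section 1.3) has a "serum pregnancy test required for women of child-bearing potential" at screening, and a local test at short-term follow-up.
- Appendix 7 tells non-postmenopausal patients to use highly effective contraception, but gives no number of months.
- Section 2.3.1 expects a negative test before starting, contraception for up to 6 months after the last imlunestrant dose, and GnRH-agonist suppression.
- Exclusion 28 bars anyone "Pregnant, breastfeeding, or expecting to conceive or father children within the projected duration of the trial", with a horizon that runs to 180 days after the last dose in every arm.

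**The concern.** Two definitions of postmenopausal status are in use, and criterion 6 is tied to neither. It is tied to the route of ovarian suppression. A woman can be postmenopausal for entry, of childbearing potential for pregnancy precautions, and still outside the criterion that carries the most specific precautions.

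Appendix 7 cites a possible risk of human teratogenicity and fetotoxicity. For women, the 2-year period after fulvestrant is stated only in criterion 6 and its country copies. The amendment history (Appendix 17) records that amendment (a) added the fulvestrant requirement to criteria 6 and 7 because it had been left out inadvertently. The sponsor therefore regarded it as important, and criterion 7b gives it to every male participant who receives fulvestrant.

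**Working it through.** The plan gives no figure on this point to reproduce. The check sets the provisions side by side and then measures the two differences.

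**Step 1: who falls between the definitions**

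| Woman entering under 5c, not permanently sterile | Criterion 5c | Appendix 7 | Criterion 6 |
|---|---|---|---|
| Aged 18 to 40 | Postmenopausal | Childbearing potential (not over 40) | Not triggered |
| Aged 41 to 59, FSH below 40 mIU/mL, local threshold below 40 | Postmenopausal | Childbearing potential (FSH too low) | Not triggered |
| Aged 41 to 59, FSH 40 mIU/mL or higher, other Appendix 7 conditions met | Postmenopausal | Postmenopausal | Not triggered, not needed |

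Criterion 5c requires amenorrhea without ovarian suppression, so entry under 5c and the criterion 6 trigger cannot overlap. The second row is empty wherever the local FSH threshold is 40 mIU/mL or higher; the documents give no local values.

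**Step 2: age of the pregnancy test at Cycle 1 Day 1**

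Inputs: screening runs from Day -28 to Day -1 (Sections 1.3 and 1.3.2). Criterion 6 counts 14 days back from enrollment, which is treatment assignment (Appendix 16). Let d be the days from randomization to Cycle 1 Day 1. The documents give no value for d, so a range is shown.

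- Oldest test under the schedule alone: 28 days.
- Oldest test under criterion 6: 14 + d days.
- Excess: 28 - (14 + d) = 14 - d days.

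| d (assumed) | Excess age of test |
|---|---|
| 0 | 14 days |
| 3 | 11 days |
| 7 | 7 days |

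**Step 3: contraception period after the last dose**

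The conversion uses the SAP's own factors (Section 4.1.1): 30.4375 days per month and 365.25 days per year. Exclusion 28's 180 days is 180 / 30.4375 = 5.9 months.

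| Treatment | Criterion 6 | What still reaches her | Difference |
|---|---|---|---|
| Imlunestrant (Arms A and C) | 6 months | 6 months in Section 2.3.1; 180 days in exclusion 28 | None |
| Exemestane (Arm B) | 6 months = 182.6 days | Appendix 7 instruction with the 180-day horizon | 182.6 - 180 = 2.6 days, immaterial |
| Fulvestrant (Arm B) | 2 years = 730.5 days | Appendix 7 instruction with the 180-day horizon | 730.5 - 180 = 550.5 days, about 18 months |

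The only material difference in duration is for fulvestrant.

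**The case against.** The strongest reply is that the documents already protect these women. All women of childbearing potential are tested at screening and at short-term follow-up, and Belgium adds on-study tests. Appendix 7 instructs contraception, and criterion 14 makes compliance with protocol requirements part of consent. Exclusion 28 sets 180 days in every arm. This stands, and it limits the point. A reader might infer that these women have no pregnancy test or no contraception requirement, or that Arm B has no stated time horizon at all; the text supports neither. Exclusion 28 is worded as a bar on expecting to conceive rather than as a contraception duration, but read with Appendix 7 it gives about 6 months. What it does not give is the 2 years for fulvestrant.

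A second reply is that Section 2.3.1 expects every woman of childbearing potential to be on a GnRH agonist, which would bring her within criterion 6. This counts as a further safeguard. It does not close the gap, because Section 2.3.1 is not an eligibility criterion. A woman who qualified under 5c would also not owe her postmenopausal status to suppression, even if she later took a GnRH agonist.

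A third reply is that the group may be nearly empty. A woman of 40 or under needs 12 months of unprovoked amenorrhea with both FSH and estradiol in the postmenopausal range. Appendix 7 also leaves permanent infertility from other causes to investigator discretion and calls for more evaluation if fertility is unclear. This is fair. A reader might take Arm B's planned 320 participants as a guide to the number affected. They are not, since they include men, older women, women on suppression and exemestane recipients.

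Finally, the consent form and the fulvestrant label are not in the reviewed text and may state a period. That is possible and cannot be checked.

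**Conclusion.** The mismatch is real and follows directly from the wording. A non-sterile woman aged 40 or under who enters under 5c, or one aged 41 to 59 with FSH below 40 mIU/mL at a site whose threshold is lower, is of childbearing potential under Appendix 7 but outside criterion 6. The consequences are narrow: a pregnancy test up to 14 days older (14 - d, with d assumed) and, for fulvestrant recipients only, the loss of the extension from about 6 months to 2 years of contraception. There is no material duration gap for imlunestrant or exemestane.

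The number of women is probably very small and cannot be derived, because no age or FSH distribution is given. Efficacy, power and alpha are not touched. This is a minor point and a cheap patient-safety improvement. Confidence in the wording mismatch is high; whether any woman would in practice miss the 2-year advice depends on documents not seen.

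**What to change.** Keep criterion 6's existing trigger and add an alternative: or if a woman of childbearing potential per Appendix 7. Make the same change in the Belgium and Germany copies. State the post-treatment period in Appendix 7 itself: 6 months, or 2 years for fulvestrant.

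Criterion 5 need not change, and no new GnRH requirement is proposed. The GnRH expectation in Section 2.3.1 should stay as it is, not be narrowed.

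The cost is wording in the next amendment, plus an occasional repeat pregnancy test when the screening test is more than 14 days old at enrollment.

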10.8. Appendix 8: Genetics

Use/Analysis of DNA

- Genetic variation may impact a participant's response to study intervention, susceptibility to, and severity and progression of disease. Variable response to study intervention may be due to genetic determinants that impact drug absorption, distribution, metabolism, and excretion; mechanism of action of the drug; disease etiology; and/or molecular subtype of the disease being treated. Assessment of variable response may include evaluation of AEs or differences in efficacy. Therefore, where local regulations and IRB/IEC allow, a blood sample will be collected for DNA analysis from consenting participants.
- DNA samples will be used for research related to imlunestrant or breast cancer and related diseases. They may also be used to develop tests/assays, including diagnostic tests related to study intervention and/or interventions of this drug class and indication. Genetic research may consist of the analysis of 1 or more candidate genes or the analysis of genetic markers throughout the genome or analysis of the entire genome (as appropriate).
- Samples may also be used to determine the somatic or germline origin of tumor-associated genetic alterations.
- Samples will not be used to conduct unspecified disease or population genetic research either now or in the future.
- The samples may be analyzed as part of a multi-study assessment of genetic factors involved in the response to imlunestrant or study interventions of this class to understand study disease or related conditions.
- The results of genetic analyses may be reported in the CSR or in a separate study summary.
- The Sponsor will store the DNA samples in a secure storage space with adequate measures to protect confidentiality.
- All samples will be coded with the patient number. These samples and any data generated can be linked back to the patient only by the investigator site personnel.
- Samples will be retained at a facility selected by the Sponsor or its designee for a maximum of 15 years after the last participant visit for the study, or for a shorter period if local regulations and/or ERBs/IRBs impose shorter time limits. This retention period enables use of new technologies, response to regulatory questions, and investigation of variable response that may not be observed until later in the development of imlunestrant or after imlunestrant become(s) commercially available.
- Molecular technologies are expected to improve during the 15-year storage period and therefore cannot be specifically named. However, existing approaches include whole genome and exome sequencing, genome wide association studies, and candidate gene studies. Regardless of technology utilized, data generated will be used only for the specific research scope described in this section.

10.9. Appendix 9: Liver Safety: Suggested Actions and Follow-Up Assessments

Hepatic Evaluation Testing

See Section 10.4, Appendix 4 and Section 8.2.2.1 for guidance on appropriate test selection.

Local testing may be performed in addition to central testing when necessary for immediate participant management.

Results will be reported if a validated test or calculation is available.

Selected tests may be obtained in the event of a treatment-emergent hepatic abnormality and may be required in follow-up with participants in consultation with the Sponsor CRP/CRS.

Hematology – local laboratory	Clinical Chemistry – central laboratory					
Hemoglobin	Total bilirubin					
Hematocrit	Direct bilirubin					
Erythrocytes (RBCs - red blood cells)	Alkaline phosphatase (ALP)					
Leukocytes (WBCs - white blood cells)	Alanine aminotransferase (ALT)					
Differential:	Aspartate aminotransferase (AST)					
Neutrophils, segmented	Gamma-glutamyltransferase (GGT)					
Lymphocytes	Creatine kinase (CK)					
Monocytes	Other Chemistry – central laboratory					
Basophils	Acetaminophen					
Eosinophils	Acetaminophen protein adducts					
Platelets	Alkaline phosphatase isoenzymes					
Cell morphology (RBC and WBC)	Ceruloplasmin					
	Copper					
Coagulation – local laboratory	Ethyl alcohol (EtOH)					
Prothrombin time, INR (PT-INR)	Haptoglobin					
Microbiology – local laboratory	Immunoglobulin A (IgA [Quantitative])					
Culture	Immunoglobulin G (IgG [Quantitative])					
Blood	Immunoglobulin M (IgM [Quantitative])					
Urine	Phosphatidylethanol (PEth)					
	Urine Chemistry – central laboratory					
	Drug screen					
	Ethyl glucuronide (EtG)					
Serology – local laboratory	Other Serology – central laboratory					
Hepatitis A virus (HAV) testing:	Anti-nuclear antibody (ANA)					
HAV total antibody	Anti-smooth muscle antibody (ASMA) ^a					
HAV IgM antibody	Anti-actin antibody ^c					
Hepatitis B virus (HBV) testing:	Epstein-Barr virus (EBV) testing:					
Hepatitis B surface antigen (HBsAg)	EBV antibody					
Hepatitis B surface antibody (Anti-HBs)	EBV DNA ^b					
Hepatitis B core total antibody (Anti-HBc)	Cytomegalovirus (CMV) testing:					

Hepatitis B core IgM antibody	CMV antibody
Hepatitis B core IgG antibody	CMV DNA ^b
HBV DNA ^b	Herpes simplex virus (HSV) testing:
Hepatis C virus (HCV) testing:	HSV (Type 1 and 2) antibody
HCV antibody	HSV (Type 1 and 2) DNA ^b
HCV RNA ^b	Liver Kidney Microsomal Type 1 (LKM-1) antibody
Hepatitis D virus (HDV) testing:	
HDV antibody	
Hepatitis E virus (HEV) testing:	
HEV IgG antibody	
HEV IgM antibody	
HEV RNA ^b	

Abbreviations: CRP = clinical research physician; CRS = clinical research scientist; DNA = deoxyribonucleic acid; Ig = immunoglobulin; INR = international normalized ratio.

^a This is not required if Anti-Actin Antibody is tested.

^b Reflex/confirmation dependent on regulatory requirements and/or testing availability.

^c This is not required if Anti-smooth muscle antibody (ASMA) is tested.

